4.3.2 Clinical Laboratory Tests

A Laboratory Manual will be provided to the sites that specifies the procedures for collection, processing, storage, and shipment of samples, as well as laboratory contact information, specific to this clinical research study.

Clinical laboratory safety tests will be performed at a local laboratory at or near the investigator site. Sample tubes and sample sizes may vary depending on laboratory method used and routine practice at the site. Abnormal laboratory results after randomization should be repeated as soon as possible (preferably within 24 to 48 hours).

The following clinical laboratory tests will be performed (see [Table 4](#), [Table 5](#), and [Table 6](#)):

Serum Chemistry

- AST
- ALT
- Alkaline phosphatase (ALP)
- Calcium
- Chloride
- Creatinine
- Gamma-glutamyltransferase
- Glucose
- Potassium
- Sodium
- Total bilirubin (TBL)
- Urea

Note for serum chemistries: Tests for AST, ALT, ALP, and TBL must be conducted concurrently and assessed concurrently.

Hematology

- White blood cell (WBC) count with differential
- Red blood cell (RBC) count
- Hematocrit
- Hemoglobin
- Platelet count

Urinalysis

- Color
- Appearance
- Specific gravity
- pH
- Protein
- Glucose
- Ketones
- Blood
- Bilirubin
- Microscopy (including WBC/HPF, RBC/HPF)

Pregnancy Test (All Females of Childbearing Potential Only)

- Serum beta human chorionic gonadotropin (β hCG; Day -28 to Day -2)
- Urine hCG (on Day -1)

Other Safety Tests

- Hepatitis A immunoglobulin M antibody, and hepatitis B surface antigen
- Hepatitis C antibody screen
- Human immunodeficiency virus (HIV) antibody screen, syphilis test
- Urine Class A drug screen for amphetamines, opiates, and cocaine
- Follicle-stimulating hormone (only for women < 50 years of age who have been amenorrheic for \geq 12 months at screening)

4.3.3 Pharmacokinetic Evaluation

Blood samples to evaluate the PK of nirsevimab in serum will be collected according to the scheduled time points (see Section 4.2). The concentration of nirsevimab in serum will be measured using validated assays.

4.3.4 Antidrug Antibody Evaluation

Blood samples to evaluate ADA responses to nirsevimab in serum will be collected according to the scheduled time points (see Section 4.2). ADA samples may also be further tested for characterization of the ADA response. Evaluations will be performed using validated immunoassays.

4.4 Study or Study Component Suspension or Termination

The Sponsor reserves the right to temporarily suspend or terminate this study at any time. The reasons for temporarily suspending or terminating the study may include but are not limited to the following:

- 1 Death in any subject in which the cause of death is assessed as related to investigational product
- 2 Anaphylactic reaction that is related to investigational product (see [Appendix C](#) for a definition of anaphylaxis)
- 3 Grade 3 and/or 4 hypersensitivity AEs based on the National Cancer Institute Common Terminology Criteria for Adverse Events (NCI CTCAE, version 5.0) grading scale that are assessed as related to nirsevimab in 2 or more subjects. Refer to [Appendix B](#) for events not covered in NCI CTCAE.
- 4 Two SAEs of the same type that are assessed as related to nirsevimab
- 5 Subject enrollment is unsatisfactory
- 6 Sponsor decision to terminate development

If the Sponsor determines that temporary suspension or termination of the study is required, the Sponsor will discuss the reasons for taking such action with the Investigator (or head of the medical institution, where applicable). When feasible, the Sponsor will provide advance notice to all participating Investigators (or head of the medical institution, where applicable) of the impending action.

If the study is suspended or terminated for safety reasons, the Sponsor will promptly inform the Investigator, head of the medical institution (where applicable), and/or institution conducting the study. The Sponsor will also promptly inform the relevant regulatory authorities of the suspension/termination along with the reasons for such action. Where required by applicable regulations, the Investigator or head of the medical institution must inform the Institutional Review Board (IRB)/Independent Ethics Committee (IEC) promptly and provide the reason(s) for the suspension/termination. If the study is suspended for safety reasons and it is deemed appropriate by the Sponsor to resume the study, approval from the relevant regulatory authorities (and IRBs/IECs, when applicable) will be obtained prior to resuming the study.

4.5 Investigational Products

4.5.1 Identity of Investigational Products

The Sponsor will provide the Investigator(s) with investigational product ([Table 7](#)) using designated distribution centers.

Table 7 Identification of Investigational Products

Investigational Product	Manufacturer	Concentration and Formulation as Supplied
Nirsevimab	MedImmune	Supplied as 50 mg (nominal) per vial solution. The solution contains 100 mg/mL nirsevimab, CCI histidine/histidine-HCl, CCI arginine-HCl, CCI sucrose, CCI polysorbate 80, pH 6.0. The nominal fill volume is 0.5 mL.
Placebo	To be provided by study sites	Commercially available 0.9% (w/v) saline (sterile for human use)

HCl = hydrochloride; w/v = weight/volume.

Nirsevimab should be stored at 2°C to 8°C.

Labels will be prepared in accordance with Good Manufacturing Practice and local regulatory guidelines.

Nirsevimab will be supplied to the site in open-labelled kits. Each kit has a unique number printed on all labels within the kit (ie, the outer carton label and the label of each vial).

Refer to Section 4.6.2 for information on coding of the container for blinding purposes.

See the Pharmacy Manual, which is prepared by the Sponsor, for additional information.

4.5.1.1 Investigational Product Inspection

Each vial selected for dose preparation should be inspected. Refer to Table 7 for identification of investigational product.

If there are any defects noted with the investigational product, the Investigator and site monitor should be notified immediately. Refer to the Product Complaint section (Section 4.5.1.5) for further instructions.

4.5.1.2 Dose Preparation Steps

No incompatibilities between nirsevimab and polycarbonate or polypropylene syringes have been observed.

Nirsevimab does not contain preservatives and any unused portion must be discarded. Total in-use storage time from needle puncture of the investigational product vial to start of administration should not exceed 4 hours at room temperature. If storage time exceeds these limits, a new vial should be used.

The dose administration steps are as follows:

- 1 The required volume of nirsevimab (3 mL) will be obtained by withdrawing the contents of 6 investigational product vials into 3 appropriately sized syringes (ie, 2 vials per syringe). Normal saline placebo will be provided by the study sites and the required volume (3 mL) divided into 3 appropriately sized syringes. The maximum volume for each injection is 1 mL. Syringes used must be polycarbonate or polypropylene syringes. For ease of preparation, a 1.5 inch 19 gauge withdrawal needle should be used.
- 2 Switch the needle prior to administration.
- 3 Administer investigational product using the appropriate size needle ranging from 22 to 25 gauge and 5/8 to 1.5 inches based on subject weight, as per standard of care.

4.5.1.3 Treatment Administration

The first day of dosing is considered Day 1.

Investigational product (nirsevimab or placebo) will be supplied by an unblinded investigational product manager. Blinding will be performed at the site level to ensure that nirsevimab and placebo are indistinguishable in appearance and are not labelled to reveal treatment identity.

Investigational product (nirsevimab or placebo) should be administered IM in the central area and thicker portion of the deltoid (ie, above the level of the armpit and below the acromion) according to standard practice procedures for IM injections. The injection should be given using standard aseptic technique. The IM dose of nirsevimab or placebo should be given as 3 separate 1 mL injections. Two injections given in the same deltoid muscle must be separated by approximately 1 inch (2.54 cm). The third injection will be given in the other deltoid muscle.

4.5.1.4 Monitoring of Dose Administration

Subjects will be monitored before and after investigational product administration through assessment of vital signs (temperature, blood pressure, heart rate, and respiratory rate). All vital signs should be obtained within 60 minutes prior to dosing, and at 30 minutes (± 5 minutes) and 60 minutes (± 5 minutes) post dose.

As with any biologic product, allergic reactions to dose administration are possible. Therefore, appropriate drugs and medical equipment to treat acute anaphylactic reactions must be immediately available, and study personnel must be trained to recognize and treat anaphylaxis.

4.5.2 Additional Study Medications

No other study medications are specified for use in this clinical protocol.

4.5.3 Labeling

Labels for the investigational product will be prepared in accordance with Good Manufacturing Practice and local regulatory guidelines. Label text will be translated into local languages, as required.

4.5.4 Storage

Store investigational product at 2°C to 8°C.

4.5.5 Treatment Compliance

Investigational product is administered by study site personnel, who will monitor compliance.

4.5.6 Accountability

The Investigator's or site's designated investigational product manager is required to maintain accurate investigational product accountability records. Upon completion of the study, copies of investigational product accountability records will be returned to the Sponsor. All unused investigational product will be returned to a Sponsor-authorized depot or disposed of upon authorization by the Sponsor.

4.6 Treatment Assignment and Blinding

4.6.1 Methods for Assigning Treatment Groups

An IWRS will be used for randomization to a treatment group and assignment of blinded investigational product kit numbers. A subject is considered randomized into the study when

the Investigator notifies the IWRS that the subject meets eligibility criteria and the IWRS provides the assignment of blinded investigational product kit numbers to the subject.

Subjects will be randomized using a 3:1 ratio to receive either nirsevimab (n = 18) or placebo (n = 6).

The procedure for using IWRS is as follows:

- The Investigator or designee contacts the IWRS and provides the SID number and subject's baseline characteristic(s) used to verify that it is the same subject
- Placebo (provided by site) or a vial from a nirsevimab kit will be assigned to the subject
- Confirmation of this information is sent to the unblinded investigational product manager who prepares the investigational product to be dispensed to the subject per the response system and records the appropriate information in the investigational product accountability log

Investigational product (nirsevimab or placebo) must be administered the same day the investigational product is assigned. Total in-use storage time from needle puncture of the investigational product vial to administration should not exceed 4 hours at room temperature. If storage time exceeds these limits, a new vial should be used. If there is a delay in the administration of investigational product such that it will not be administered within the specified timeframe, the unblinded investigational product manager must be notified immediately.

4.6.2 Methods to Ensure Blinding

This is a double-blind study in which the site is using commercially available saline as the placebo. Nirsevimab and placebo are visually indistinguishable once in syringes. Neither the subject nor the Investigator or any of the site staff who are involved in the treatment or clinical evaluation of the subjects will be aware of the treatment received (ICH E9). In the event that treatment allocation for a subject becomes known to the Investigator or other blinded study staff involved in the management of study subjects, the Sponsor must be notified *immediately*. If the treatment allocation for a subject needs to be known to treat an individual subject for an AE, the Investigator must notify the Sponsor *immediately*. The site will maintain a written plan detailing which staff members are blinded/unblinded and the process of investigational product preparation and administration used to maintain the blind.

4.6.3 Methods for Unblinding

4.6.3.1 Unblinding in the Event of a Medical Emergency

In the event of a medical emergency, the Investigator may unblind an individual subject's investigational product allocation. Instructions for unblinding an individual subject's investigational product allocation are contained in the IWRS manual. In general, unblinding

should only occur if management of the medical emergency would be different based on the subject having received investigational product. In the majority of cases, the management of a medical emergency would be the same whether or not investigational product was received by the subject. If this was the case, the investigational product allocation should not be unblinded. In the event there is unblinding, the Investigator should promptly document and explain to the Sponsor the reason for any premature unblinding.

The Sponsor retains the right to unblind the treatment allocation for SAEs that are unexpected and are suspected to be causally related to an investigational product and that potentially require expedited reporting to regulatory authorities.

4.7 Restrictions During the Study and Concomitant Treatment(s)

The Investigator must be informed as soon as possible about any medication taken from the time of screening until the final study visit. Any concomitant medication(s), including herbal preparations, taken during the study will be recorded in the electronic case report form (eCRF).

4.7.1 Permitted Concomitant Medications

Investigators may prescribe concomitant medications or treatments which is considered necessary for the subject's safety and well-being. Specifically, subjects may receive contraceptives during the study.

4.7.2 Prohibited Concomitant Medications

Other than contraceptives, use of concomitant medications including over-the-counter medications, herbal supplements, vitamins, etc from Day 1 through Day 15 post dose is discouraged. Subjects must be instructed not to take any medications, including over-the-counter products, without first consulting with the Investigator.

4.8 Statistical Evaluation

4.8.1 General Considerations

Tabular summaries will be presented by treatment group. Categorical data will be summarized by the number and percentage of subjects in each category. Continuous variables will be summarized by descriptive statistics. Additional details of statistical analyses will be described in the statistical analysis plan.

The PK Population will include all subjects who have received any dose of investigational product, and have at least one measurable post-dose serum PK observation and for whom PK blood samples are assumed not to be affected by factors such as important protocol deviations (to be determined prior to unblinding). PK analyses will be based on the PK Population.

The As-treated Population will include all subjects who are randomized into the study and who receive any amount of investigational product. Subjects will be included in the treatment group corresponding to the treatment actually received. Safety and ADA analyses will be based on the As-treated Population.

4.8.2 Sample Size

This study will randomize approximately 24 subjects of whom approximately 18 will receive nirsevimab and approximately 6 will receive placebo. Because all analyses will be descriptive in nature and no hypothesis is being tested statistically, no formal sample size calculation was performed. Current sample size and sampling scheme are selected to facilitate estimation and numerical comparison of C_{max} , time to maximum observed concentration (T_{max}), and area under the concentration-time curve from time 0 to 150 days (AUC_{0-150}) between Chinese and non-Chinese adult subjects.

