1.4.1 Phase 1a Study D5290C00001

Study D5290C00001 was a first-time-in-human Phase 1a, randomized, double-blind, placebo-controlled, dose-escalation study conducted to evaluate the safety, tolerability, PK, and ADA of nirsevimab compared to placebo in healthy adult volunteers (Griffin et al 2017). This study was completed in June 2015. A total of 136 subjects were randomized and received a single fixed dose of nirsevimab (6 subjects each at doses of 300 mg IV, 1000 mg IV, 3000 mg IV, 100 mg IM, and 78 subjects at 300 mg IM) or placebo (34 subjects). All subjects were followed for approximately 360 days after dosing.

Safety

The safety profile of nirsevimab was favorable, with similar proportions of treatment-emergent adverse events (TEAEs) reported in the placebo (61.8%) group and the nirsevimab (62.7%) total group. Two treatment-emergent serious adverse events (TESAEs; gunshot wound and appendicitis) were reported in 2 nirsevimab subjects. TEAEs judged to be related to investigational product were reported in 29.4% of subjects in the placebo group, and 17.6% of subjects in the nirsevimab total group. The most frequent TEAEs in the nirsevimab total group included upper respiratory tract infection (URTI; 18.6%); headache (8.8%); urinary tract infection (5.9%); and dermatitis contact, musculoskeletal pain, nausea, and vomiting (4.9% each). The most frequently occurring TEAEs in the placebo group were headache (17.6%); URTI (8.8%); and nausea, increased blood creatine phosphokinase level, and paresthesia (5.9% each). There were no adverse events of special interest (AESIs) or new onset chronic diseases (NOCDs). There were no deaths. No safety signals in this healthy adult population were observed. These results demonstrated an acceptable safety profile for nirsevimab, including no observed hypersensitivity reactions, and supported further clinical studies of IM administration of 1 dose of nirsevimab in the target population of infants to provide protection for the duration of the RSV season.

Pharmacokinetics

A 2-compartment PK model adequately described the PK profile following both IV and IM administrations. Body weight was determined to be a significant covariate on systemic clearance and volume of distribution with allometric exponents. The mean population

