1.7.1 Primary Hypothesis

The PK profile of nirsevimab assessed up to 150 days after dose administration in Chinese subjects will be similar to subjects with different racial and ethnic backgrounds.

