4.8.3 Analysis of Pharmacokinetics

Serum concentrations of nirsevimab at selected time points will be evaluated to confirm that adequate exposures are maintained after dosing. Nirsevimab serum concentration data will be presented in descriptive statistics. Serum PK parameters such as C_{max} , T_{max} , and AUC_{0-150} will be estimated using noncompartmental analysis and summarized with descriptive statistics. The estimated PK parameters from the adult Chinese subjects from this study will be compared for similarity with those obtained from non-Chinese adult subjects from the global Phase 1a Study D5290C00001. This PK comparison will be presented separately from the clinical study report. Notably, regression-dependent PK parameters such as $t_{1/2}$ and apparent systemic clearance will not be estimated due to the limited sampling up to 150 days which would require at least 40% extrapolation of the total $AUC_{0-\infty}$. Nonetheless, the predictability and consistency of the PK properties of nirsevimab as demonstrated in 102 adults in the Phase 1a Study D5290C00001 and 984 infants in the Phase 1b/2a Study D5290C00002 and Phase 2b Study D5290C00003 support the hypothesis that the apparent clearance and other regression-dependent PK parameters should be similar if the C_{max} , T_{max} , and AUC_{0-150} are shown to be similar.

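### The comparison that answers the primary hypothesis has no effect measure, interval or named comparator dose group; a ratio with a 90% CI would supply them without a formal test or extra subjects

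*Supplement*

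**What the plan says.** Section 1.7.1 states the primary hypothesis: the PK profile up to 150 days "in Chinese subjects will be similar to subjects with different racial and ethnic backgrounds". Section 1.7 adds that nothing is formally tested.

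On the sample size, section 4.8.2 says "Because all analyses will be descriptive in nature and no hypothesis is being tested statistically, no formal sample size calculation was performed". It continues: "Current sample size and sampling scheme are selected to facilitate estimation and numerical comparison of" Cmax, Tmax and AUC0-150 between Chinese and non-Chinese adults. The plan is 18 subjects on nirsevimab and 6 on placebo.

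On the method, section 4.8.3 says "Nirsevimab serum concentration data will be presented in descriptive statistics", and that the PK parameters will be estimated by noncompartmental analysis and summarized descriptively. The parameters "will be compared for similarity with those obtained from non-Chinese adult subjects from the global Phase 1a Study D5290C00001". It adds: "This PK comparison will be presented separately from the clinical study report".

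Phase 1a had five active dose and route groups (section 1.4.1). Only one matches this study, with "78 subjects at 300 mg IM". Section 4.8.3 does not say that this is the comparator.

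**The concern.** The comparison has to carry a good deal. Section 3.2.3 treats similarity of Cmax, Tmax and AUC0-150 as assurance that efficacious exposures are similar. Section 4.8.3 goes on to infer similar clearance, which this study will not estimate, once those three parameters have been shown to be similar. Sections 1.5 and 3.2.2 say that the results will support registration in China.

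Two sets of means or medians do not show how large a difference the data still allow. Suppose the observed ratio were 0.90, with a CV of 30%. From the widths worked out below, the 90% CI would be 0.90 x 0.880 = 0.79 to 0.90 x 1.136 = 1.02. A reader given only the point summaries sees exposure 10% lower. That reader cannot tell that the data are compatible both with exposure 21% lower and with no reduction at all. Whether that counts as similar would be decided after the results are known, with no agreed quantity to look at.

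**Working it through.** **The plan's own figures.** The protocol states no power, precision or similarity limit, so only the counts can be reproduced. 24 x 3/4 = 18 and 24 x 1/4 = 6. Phase 1a: 4 x 6 + 78 = 102 on nirsevimab, and 102 + 34 = 136 in all. These agree with sections 4.8.2, 4.8.3 and 1.4.1.

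**Inputs for the interval.**
- n1 = 18 (section 4.8.2).
- n2 = 78 at most (section 1.4.1, 300 mg IM). How many of these are non-Chinese and PK-evaluable is not stated.
- Between-subject CV: no adult value is printed for Cmax or AUC0-150, so 20% to 40% is assumed.

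**Is 20% to 40% reasonable?** Table 3 gives adult 300 mg IM medians and maxima. If the values are log-normal with n = 78, the expected largest standard normal deviate is 2.417, so the log-scale SD is about ln(max/median)/2.417:
- Cmax: ln(78.4/45.8)/2.417 = 0.222, a CV of about 23%.
- AUC0-infinity: ln(9,956/4,917)/2.417 = 0.292, a CV of about 30%.

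A single maximum is a weak basis. The 5th and 95th percentiles of that deviate are 1.778 and 3.214. They put the CV at about 17% to 31% for Cmax and 22% to 41% for AUC0-infinity. The one AUC CV in the protocol is 35.0%, for AUC0-infinity in preterm infants (section 1.4.3).

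**Formula.** s = sqrt(ln(1 + CV²)); h = t(0.95; n1 + n2 - 2) x s x sqrt(1/n1 + 1/n2); limits around a ratio of 1 are exp(-h) and exp(h).

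For 18 versus 78, t(0.95; 94) = 1.661 and sqrt(1/18 + 1/78) = 0.2615.

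| CV | s | h | 90% limits |
|---|---|---|---|
| 20% | 0.198 | 0.086 | -8.2% / +9.0% |
| 25% | 0.246 | 0.107 | -10.1% / +11.3% |
| 30% | 0.294 | 0.128 | -12.0% / +13.6% |
| 35% | 0.340 | 0.148 | -13.7% / +15.9% |
| 40% | 0.385 | 0.167 | -15.4% / +18.2% |

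**Sensitivity to the counts.** The 18 Chinese subjects supply most of the variance: (1/18)/(1/18 + 1/78) = 0.0556/0.0684 = 81%. Losing comparators therefore matters little. With 18 versus 40, the limits are -9.0%/+9.9% at CV 20% and -16.7%/+20.1% at CV 40%. With 15 versus 78, they are -8.9%/+9.7% at CV 20% and -14.7%/+17.3% at CV 35%.

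**What the interval leaves out.** Section 1.4.1 reports body weight as a significant covariate on clearance and volume in Phase 1a. This study admits 45 to 110 kg with a BMI of 19 to 26 kg/m² (section 4.1.2), and the Phase 1a weight distribution is not given. An unadjusted ratio therefore mixes ethnicity with weight and with other differences between the studies.

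**The case against.** The strongest reply is that this is a small descriptive study, and that section 4.8.1 leaves further detail to the SAP, which is not among the documents. A ratio with an interval may be planned there or in the plan for the separate comparison. This stands in part. The protocol nowhere excludes a ratio, and a ratio is itself a numerical comparison. A reader might infer that the protocol commits to a bare side-by-side display, but the text does not say so. What remains is that the protocol gives the sample-size rationale and the weight placed on the comparison, yet names neither the quantity to be estimated nor its expected precision. It also moves the comparison out of the CSR without saying which plan governs it. An interval is estimation, so it does not conflict with the decision not to test.

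A reader might also infer that the CSR will lack the primary result. It will not. The primary endpoint in section 2.1 is a summary of concentrations and PK parameters within this study. Only the cross-study comparison is placed elsewhere, and section 4.8.3 says so openly.

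Finally, a reader might suspect that Phase 1a was sampled more densely, which would raise its Cmax, or that no Phase 1a AUC0-150 exists because Table 3 gives AUC0-infinity. The documents support neither. The Phase 1a schedule is not shown, Table 3 serves the dose rationale, and section 4.8.2 says that the sampling scheme was chosen with this comparison in mind.

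**Conclusion.** The point holds in a limited form. The primary hypothesis is comparative, but the protocol names no effect measure, no interval and no Phase 1a dose group for the comparison. Point summaries alone would not support the conclusions drawn in sections 3.2.3 and 4.8.3.

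The planned size is adequate for an informative estimate: about -8%/+9% at CV 20% to -15%/+18% at CV 40%, with 18 versus up to 78 subjects. This rests on assumed CVs, on log-normality, on AUC0-infinity being a fair guide to the variability of AUC0-150, and on nearly all 78 comparators being non-Chinese and PK-evaluable. The last assumption matters least.

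It would be too strong to say that the interval separates chance from a true ethnic difference. It describes sampling error only, and weight and between-study differences remain even when it is narrow.

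**What to change.** - **Section 4.8.3, measure.** State that for Cmax and AUC0-150 the geometric mean ratio (this study / non-Chinese Phase 1a subjects given 300 mg IM) will be estimated from individual data with a 90% CI, both unadjusted and adjusted for baseline body weight. Compare Tmax by medians.
- **Section 4.8.3, derivation.** Derive Cmax and AUC0-150 in both studies over nominal sampling days common to both, where the Phase 1a schedule allows.
- **Section 4.8.2.** Add the expected CI width as a conditional statement: the limits above for CVs of 20% to 40%, with the CVs labelled as assumptions and a note that the interval does not cover between-study differences.
- **Reporting.** The comparison may stay outside the CSR, provided that its method is prespecified and the CSR cross-refers to it.

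The cost is a few sentences and a little more analysis work on individual data from a completed study in the same programme. No formal test and no extra subjects are needed.
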